Inaccurate deployment of the iCast covered, balloon expandable branch vessel stent due to mal-rotation or inaccurate placement may lead to vessel occlusion and end organ or limb ischemia. Although the risk of inaccurate deployment can be mitigated by careful case planning, pre-cannulated wires to aid positioning, and use of radiopaque alignment markers, mal-rotation or inaccurate placement may still occur.

Failure to deploy the iCast covered, balloon expandable branch vessel stent may result in increased procedural time, conversion to open, or procedural failure. The risk can be mitigated by having additional components available and having tools prepared to perform open surgical repair if necessary.

Displacement of the thoracic bifurcation due to incomplete apposition of the stent graft, non-compatible or damaged components/accessories, or size mismatch can result in endoleak, aneurysm enlargement, aneurysm rupture, vessel occlusion, end organ or limb ischemia. Although the risk can be mitigated with the use of careful case planning, strict adherence to the investigation procedure, completion angiograms, regular follow-ups, and treatment with cuffs, ballooning, or additional stent grafts, the risk of displacement still exists.

Displacement of the visceral manifold due to incomplete apposition of the stent graft, non-compatible or damaged components/accessories, or size mismatch can result in endoleak, aneurysm enlargement, aneurysm rupture, vessel occlusion, end organ or limb ischemia. Although the risk can be mitigated with the use of careful case planning, strict adherence to the investigation procedure, completion angiograms, regular follow-ups, and treatment with cuffs, ballooning, or additional stent grafts, the risk of displacement still exists.

Displacement of the visceral bypass due to incomplete apposition of the stent graft, non-compatible or damaged components/accessories, or size mismatch can result in endoleak, aneurysm enlargement, aneurysm rupture, vessel occlusion, end organ or limb ischemia. Although the risk can be mitigated with the use of careful case planning, strict adherence to the investigation procedure, completion angiograms, regular follow-ups, and treatment with cuffs, ballooning, or additional stent grafts, the risk of displacement still exists.

Displacement of the infrarenal bifurcation due to incomplete apposition of the stent graft, non-compatible or damaged components/accessories, or size mismatch can result in endoleak, aneurysm enlargement, aneurysm rupture, vessel occlusion, end organ or limb ischemia. Although the risk can be mitigated with the use of careful case planning, strict adherence to the investigation procedure, completion angiograms, regular follow-ups, and treatment with cuffs, ballooning, or additional stent grafts, the risk of displacement still exists.

Displacement of the iliac limbs due to incomplete apposition of the stent graft, non-compatible or damaged components/accessories, or size mismatch can result in endoleak, aneurysm enlargement,

aneurysm rupture, vessel occlusion, end organ or limb ischemia. Although the risk can be mitigated with the use of careful case planning, strict adherence to the investigation procedure, completion angiograms, regular follow-ups, and treatment with cuffs, ballooning, or additional stent grafts, the risk of displacement still exists.

Displacement of the iCast covered, balloon expandable branch vessel stent due to incomplete apposition of the stent graft, non-compatible or damaged components/accessories, or size mismatch can result in endoleak, aneurysm enlargement, aneurysm rupture, vessel occlusion, end organ or limb ischemia. Although the risk can be mitigated with the use of careful case planning, strict adherence to the investigation procedure, use of industry standard seal zone lengths and oversizing, completion angiograms, regular follow-ups, treatment with cuffs, ballooning, or additional stent grafts, the risk of displacement still exists.

Inadvertent internal iliac occlusion and ischemic colitis due to vessel occlusion can occur. The risk can be mitigated with the use of careful case planning, using proper endovascular technique, completion angiograms, and regular follow-ups.

Device-related risks

There are device-related risks of the modular components succumbing to material fatigue resulting in component separation, endoleak, kinking, or migration. These risks can be mitigated several ways including adhering to industry standard seal zone lengths, proper oversizing, lining branch stents with self-expanding stents, regular follow-ups to identify early evidence of migration or separation and allow for appropriate treatment, by the use of completion angiography coupled with cuffs, ballooning, or additional stent grafts if evidence of endoleak.

Migration can occur when a stent graft is deployed with inadequate landing zone, improper oversizing, resulting in vessel occlusion, endoleak, aneurysm enlargement, or aneurysm rupture. Although the risk of migration can be mitigated by using industry accepted overlaps, proper oversizing, accepted suture techniques, and adhering to the follow up schedule, it can still occur.

Component separation can occur when a stent graft is deployed with improper overlap, improper oversizing, or when a suture line fails, resulting in vessel occlusion, endoleak, aneurysm enlargement, or aneurysm rupture. Although the risk of component separation can be mitigated by using industry accepted overlaps, proper oversizing, accepted suture techniques, and adhering to the follow up schedule, it can still occur.

Graft occlusion due to angulation, kink, or mal-alignment modular components can lead to implant thrombosis. Using careful case planning for appropriate sizing, adherence to the investigational protocol, lining with self-expanding stents and regular patient follow-up can mitigate this risk, but graft occlusion can still occur.

Endoleak and endotension due to inadequate seal between graft and components, graft permeability, poor graft seal, improper oversizing, suture line holes, or graft wear can result in aneurysm enlargement, aneurysm rupture, or retrograde flow from branch arteries. Although the risk can be mitigated with completion angiograms, regular follow-ups, and treatment with secondary procedures or devices (cuffs, balloons, and stents), endoleak or endotension can still occur.

Graft infection can result in fever, sepsis, and conversion to open repair. The risk can be mitigated by following the investigational protocol, administering post-operative blood tests to monitor condition, use of antibiotics, and regular follow-up. Even with these mitigation strategies the risk of graft infection still exists.

Branch stent graft kink or crush can result from aneurysm sac remodeling, stent graft migration, or fatigue of implant. Although the risk can be mitigated by lining the bridging stents with self-expanding bare metal stents, kink can still occur. And if it does it may result in vessel occlusion or embolism.

Aortic stent graft kink may result in misalignment of kink of components ultimately resulting in vessel occlusion or embolism. Although the risk can be mitigated by careful case planning, proper subject selection, lining bridging stents with self-expanding stents, adherence to the investigational protocol, and regular subject follow-ups, it can still happen.

Stent breakage due to manufacturer flaw, fatigue, poor placement of stent, or compatibility with other components can result in vessel occlusion, embolism, migration, separation, vascular trauma, and vessel rupture. Although the risks can be mitigated with the use of careful case planning for placement and sizing, proper oversizing, use of compatible components, and regular follow-up, stent breakage can still occur.

Branch vessel stent crush due to aneurysm remodel, longitudinal or rotational movement, placement, fixation, or material fatigue and subsequent decreased kink resistance can result in branch vessel occlusion, lumen obstruction, end organ or limb ischemia. These can be mitigated with the use of careful case planning for appropriate sizing, adherence to the investigational protocol, lining bridging stents with self-expanding stents to increase radial resistance, and regular follow-up.

Barb fracture/separation due to placement, fixation, or fatigue can result in migration, separation, vascular trauma, or embolism. This can be mitigated with the use of careful case planning for subject selection and regular follow-up.

Fabric wear due to material fatigue can result in endoleak, component separation, or migration. Using proper placement of devices and regular follow-up, but fabric wear can still occur.

Type III endoleak due to a defect in the graft or inadequate seal between modular graft components can lead to aneurysm enlargement, aneurysm rupture, or retrograde flow from branch arteries. Although the risk can be mitigated with careful construction of the grafts, proper seal between grafts, completion angiograms, regular follow-ups, and treatment with secondary procedures or devices (cuffs, balloons, and stents), endoleaks can still occur.

Biocompatibility risks due to use of materials that are not biocompatible can lead to adverse reactions in subjects. This can be mitigated by only using commercially available materials that have acceptable biocompatibility profiles. Even with these mitigation strategies, adverse reactions can occur.

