The need for a redo procedures in TAAA repair is common and is primarily due to extension of the aneurysmal disease¹⁸. Other causes for a late redo procedure include including para-anastomic aneurysms, pseudo-aneurysms, stent graft migration, type I endoleaks, graft infection, or fistulas¹⁹. Natural history studies and literature reviews cite an incidence rate of 25-60% for patients developing further aneurysmal changes after aortic repair. One center reported the rate of redo operations on TAAA repair to be 14%¹⁸.

Aneurysms with Obstructive Stenting

Patients suffering from thoracic and abdominal aortic aneurysms can benefit from the proven safety and efficacy of open surgical and endovascular stent grafting. However, the repair does not halt disease progression and may lead to future aneurysmal formation in adjacent segments of the aorta. The continued expansion necessitates revision to mitigate the risk of pending rupture. The incidence of revision following aneurysm repair is between 2.4-5.2%²⁰ in abdominal aortic aneurysms and 14% in thoracoabdominal aortic aneurysms (TAAA)¹⁸.

Treatment Options

Medical Management

Medical management of both fusiform thoracoabdominal aneurysms and type B aortic dissections includes normalizing blood pressure to prevent further dilation or dissection. Close monitoring should be performed. Operation should be limited to patients whose aneurysms are at least 5.5-cm in diameter, whose symptoms persist, whose aneurysms enlarge and are at least 4.5-cm in diameter, or who develop evidence of bleeding. But if any of those conditions are observed (persistent symptoms, aneurysm enlargement, and evidence of bleeding), the patient should be offered repair. For dissections operation is suggested for symptomatic patients and those with complications including malperfusion syndrome or active hemorrhage. For prior repair, if there are persistent endoleaks, loss of seal, or device integrity issues of previously placed graft material repair should be offered.

Open Surgical Repair

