Treatment of TAAA aneurysms in all patients that meet entry criteria will be considered for this study. All patients diagnosed with a TAAA repair are considered high risk due to the natural history of a patient with a TAAA. Their options are limited for endovascular repair and due to the comorbidities in this population they are all high risk open repair. Additionally, all patients undergoing open surgical repair of a thoracoabdominal aneurysm are considered to be at high risk for comorbidities and complications. Based on initial clinical experience, we believe that we can treat all patients with outcomes better to those of open surgical repair with less cost over the year. The current approach is an endovascular repair with lower surgical morbidity and mortality rate compared to open repair. Endovascular repair may also decrease the recovery time and length of hospital stay. From the initial clinical evaluation, certain patients may not be a good candidate for this approach have been identified. This patient population includes patients presenting emergently, with compromised renal access, or dissections. The inclusion and exclusion criteria for this study has been refined to present a patient population that we feel may significantly benefit from this

procedure without undue risk. The inclusion criteria listed in section 6 including aneurysm characteristics, access vessel morphology, minimum neck length, diameter of aneurysm, branch vessel size, patency of the four major visceral vessels, and size of distal fixation site are required as inclusion criteria to achieve an adequate seal zone and optimal placement with the stent graft and branches.

The patient population being excluded from this study includes patients with a ruptured aneurysm (or contained rupture), obstructive stenting of the visceral vessels, or a dissection in the treated portion of the aorta. Also patients with thrombus or excessive calcification within the neck of the aneurysm will be excluded as they put the patient at high risk of aneurysmal rupture or embolic event during surgical manipulation. Anatomy that does not allow for primary or assisted patency of the left subclavian artery will be excluded because it is required for access. Additionally, anatomy that would not allow for maintenance of at least one patent hypogastric artery will be excluded in order to prevent organ and/or pelvic ischemia and paraplegia.

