The device can be used as an off-the-shelf system, negating the need for lead times associated with custom-built devices. The critical sizing that will need to be done is with the proximal end of the thoracic bifurcation, distal landing zone in the aorta or iliac arteries, and the bridging stents. The proximal end of the thoracic bifurcation can be sized by choosing any of the available sizes of the Medtronic TAAA thoracic bifurcation stent grafts, and the sizes of the bridging stents can be manipulated by choosing any of the commercially available sizes of the Atrium iCast. The Atrium iCasts are added to the system in-vivo and connected with passive fixation which negates the need to size the main body components based on the

target vessel sizes. All other connections in the device make use of sizes that are the same, independent of patient anatomy.

The deployment of this device is also independent of device alignment. Angular alignment of the thoracic bifurcation and the visceral manifold has very little impact on the outcome of the case. Longitudinal alignment is more important, but a safety factor has been built-in by calling for the distal ends of the visceral manifold to be deployed above their target vessels by 1-2 cm. The longitudinal landing should be optimized so that the graft is not landed too low so that the connection with the visceral vessels is challenging to make.

[figure not shown]

Figure 2: Assembly drawing showing the thoracic bifurcation, the visceral manifold, the branch stents, and the infrarenal grafts, all deployed within an idealized aneurysm sketch.

Intended Use/Indications for Use

The Valiant Thoracoabdominal Stent Graft System is indicated for the endovascular treatment of thoracoabdominal aortic aneurysm (Crawford Type 1, 2, 3 and 5) in patients with the following characteristics:

- An aneurysm with a maximum diameter of > 5.5 cm or 2 times the normal diameter just proximal to the aneurysm using orthogonal (i.e., perpendicular to the centerline) measurements
- Aneurysm with a history of growth > 0.5 cm in 6 months
- Saccular aneurysm deemed at significant risk for rupture
- Symptomatic aneurysm greater than or equal to 4.5 cm
- Axillary or brachial and iliac or femoral access vessel morphology that is compatible with vascular access techniques, devices or accessories, with or without use of a surgical conduit
- Proximal landing zone for the thoracic bifurcation stent graft that has:

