The outcomes from prior clinical evaluation of the study device, including successfully treating 99% (84/85) of the intended target vessels and 96% (27/28) limb patency observed at one year, demonstrate the potential benefits of the device. When contrasted with open repair's significant complication rates and branch fenestrated device's significant anatomic and logistic limitations, the potential risk of the proposed novel graft does not outweigh the potential benefit of widened anatomic availability and improved patency rates. Given the potential benefits, we feel that it is justified to expose the target patient population to the potential risk. The non-clinical testing performed by Medtronic and the clinical results reported by Sanford Health show adequate safety of the device to support a durable comparison of longitudinal cost and patient centered outcomes for patients treated with the Medtronic Valiant Thoracoabdominal Stent Graft System, and provide a valid comparison of open and endovascular surgical outcomes for TAAA patients.

4. Study Procedures

- a. Study design, including the sequence and timing of study procedures (distinguish research procedures from those that are part of routine care).

Patient Population

The study will evaluate 16 patients with type I, II, III, and V thoracoabdominal aneurysms meeting protocol inclusion criteria. The patient population includes both male and female patients greater than 18 years old with a life expectancy of at least one year.

Study Type and Duration

This study is a prospective, single-center, non-randomized, multi-arm study to evaluate the therapeutic benefit of the Valiant Thoracoabdominal Stent Graft System. A total of 16 patients (10 in the primary study arm; 6 in the expanded selection criteria arm) will be enrolled in the study for treatment with the Valiant Thoracoabdominal Stent Graft System. The duration of the investigation is anticipated as follows:

- Time to Complete Enrollment: 24 months
- Subject Follow-up Time: 5 years from last subject enrollment
- Total Duration Time: 7 years

Intended Use

The Valiant Thoracoabdominal Stent Graft System is indicated for the endovascular treatment of thoracoabdominal aortic aneurysm (Crawford Type 1, 2, 3 and 5) in patients with the following characteristics:

- o An aneurysm with a maximum diameter of > 5.5 cm or 2 times the normal diameter just proximal to the aneurysm using orthogonal (i.e., perpendicular to the centerline) measurements

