 - Access vessels for compatibility with vascular access techniques
 - Obstructive stenting of the visceral vessels
 - Vessels diameters suitable for use with the Valiant Thoracoabdominal Stent Graft System
 - Aneurysm rupture
 - Dissection
 - Patency of left subclavian artery, hypogastric arteries, lumbar arteries, and all four visceral vessels
 - Thrombus or excessive calcification in the neck of the aneurysm
 - Presence and location of any previously placed graft material
- Complete blood count to evaluate white blood cells, hemoglobin, and platelets
- Basic metabolic panel to evaluate creatinine
- For patients with a history of smoking a pulmonary function test
- Cardiac clearance

Case Planning

From the pre-op CT, the surgeon will make the following measurements to size the endografts.

1. Length of the proximal seal zone, the distance required to land the thoracic bifurcation stent graft, this requires ≥ 2.5 cm section of healthy aorta or previously placed graft material, distal to the left subclavian artery or ≥ 2.5 cm of surgical graft.
2. Diameter of the proximal landing zone to define the required diameter of the thoracic bifurcation stent graft. The diameter of the thoracic bifurcation stent graft should be 10-15% larger than the diameter of the aorta to proper oversize the stent graft.
3. Maximum aortic diameter within the treated aorta
4. Distance from the top of the celiac to the top of the most cephalic renal.
5. Distance from the top of the proximal seal zone to the takeoff of the celiac.
6. Distance from the top of the celiac to the SMA.
7. Angulation at the mid-thoracic aorta.
8. Angulation at the diaphragm.
9. Angulation at the renal arteries.
10. Distance from the right renal to the ipsilateral internal iliac artery.
11. Distance from lower renals to aortic bifurcation.
12. Diameter of the branch vessels (celiac, SMA, left renal, and right renal) to determine the diameter bridging stents needed and percent patency.
13. Diameter of the right and left common iliac to secure the distal seal of the infrarenal bifurcation.
14. Diameter of the distal aorta to secure the distal seal in aorta

15. Minimum diameter of the access sites (right and left femoral and brachial access site).
16. Length from the access sites to the target treatment zone (right and left femoral and brachial access site).
17. Length between distal edge of LSA and start of aneurysm
18. Length of proximal seal zone
19. Length of aneurysm

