N/A

g. Description of what happens to participants receiving therapy when study ends or if a participant's participation in the study ends prematurely.

N/A

5. Inclusion/Exclusion Criteria

Modified Inclusion Criteria

A patient may be entered into the study if the patient has at least one of the following:

- An aneurysm with a maximum diameter of ≥ 5.5 cm or 2 times the normal diameter just proximal to the aneurysm using orthogonal (i.e., perpendicular to the centerline) measurements
- Aneurysm with a history of growth ≥ 0.5 cm in 6 months
- Saccular aneurysm deemed at significant risk for rupture
- Symptomatic aneurysm greater than or equal to 4.5 cm
- Axillary or brachial and iliac or femoral access vessel morphology that is compatible with vascular access techniques, devices or accessories, with or without use of a surgical conduit
- Proximal landing zone for the thoracic bifurcation stent graft that has:
 - ≥ 2.5 cm of healthy/nondiseased tissue (including previously placed graft material) (neck) distal to the left subclavian artery (LSA) and a diameter in the range of 26-42 mm
 - Adequate distance from the celiac artery, in order to accommodate cannulation from the antegrade access point when considering the total deployed length of the thoracic bifurcation and visceral manifold
- Minimum branch vessel diameter greater than 5 mm
- Iliac artery distal fixation site, including both native tissue and previously placed graft, greater than or equal to 15 mm in length and diameter in the range of 8 – 25 mm
- Age: ≥ 18 years old
- Life expectancy: > 1 year

Exclusion Criteria

General exclusion

- Patient is a good candidate for and elects open surgical repair
- Can be treated in accordance with the instructions for use with a legally marketed endovascular prosthesis
- Is eligible for enrollment in a manufacturer-sponsored IDE at the investigational site
- Unwilling to comply with the follow-up schedule
- Inability or refusal to give informed consent by patient or legal representative
- Patient is pregnant or breastfeeding
- Patient has a contained rupture
- Patient has a ruptured aneurysm
- Patient has a dissection in the portion of the aorta intended to be treated
- Obstructive stenting of any or all of the visceral vessels
- Poor performance status including two major system failures (including but not limited to cardiovascular, pulmonary, renal, hepatobiliary, and neuromuscular)

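### The section 5 inclusion list lets any one of ten items suffice, which contradicts section 3, where several anatomical items are called required; the list needs splitting, with linked wording settled in the same amendment

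*Combined protocol and SAP*

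**What the plan says.** Section 5, Modified Inclusion Criteria, begins: "A patient may be entered into the study if the patient has at least one of the following". Ten top-level items follow, with no second lead-in and no joining word that would divide them.

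Section 3, Justification for Specific Patient Selection Criteria, treats much of the same content as mandatory. It names aneurysm characteristics, then "access vessel morphology, minimum neck length, diameter of aneurysm, branch vessel size", and ends with "patency of the four major visceral vessels, and size of distal fixation site are required as inclusion criteria". It introduces these as "The inclusion criteria listed in section 6", although the criteria stand in section 5.

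Section 4, Case Planning, says of the proximal seal zone that "this requires ≥ 2.5 cm section of healthy aorta or previously placed graft material". Section 4, Patient Population, adds: "The patient population includes both male and female patients greater than 18 years old with a life expectancy of at least one year".

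The Intended Use lists in sections 3 and 4 repeat most of the items under the lead-in "Crawford Type 1, 2, 3 and 5) in patients with the following characteristics". That wording says neither any nor all, so it does not settle the logic.

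**The concern.** Section 5 is the operative eligibility list, and Source Document Verification in section 8 has the monitor review trial eligibility in the first five charts. A failure there triggers review of five more. That check needs a list whose logic is determinate. As written, the list does not make its anatomical items mandatory, and a reader has to find that in background and planning text.

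The boundary between arms also matters for analysis. Section 7C keeps the primary and expanded arms separate and pools the data with other physician-sponsored studies of the same device. The primary arm has 10 patients, so one misassigned patient would be 1/10 = 10% of it.

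**Working it through.** This is a check of logic, so the passages are set side by side. The list has 4 + 6 = 10 items.

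| Section 5 item | Called required in section 3, Justification? | Other text that would enforce it |
|---|---|---|
| Four indications (size, growth, saccular, symptomatic) | Diameter and, generally, aneurysm characteristics | None among the exclusions |
| Access morphology | Yes | In part: the left subclavian exclusion; screening CT evaluates access vessels |
| Proximal landing zone (length, diameter 26-42 mm, celiac distance) | Length only | Case Planning requires length of at least 2.5 cm; the neck exclusion concerns thrombus and calcification |
| Branch diameter above 5 mm | Yes | Under 5 mm is barred from the primary arm in section 3 (small branch vessels) and section 5 (Expanded Selection) |
| Distal fixation site | Yes | None among the exclusions |
| Age | Not named | Patient Population statement only |
| Life expectancy | Not named | Patient Population statement only |

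**Literal reading.** Any single row meets the list, including age. That conflicts with section 3 for access, neck length, branch size and distal fixation. Case Planning supports the conflict only for seal length; its other entries are measurements.

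**Changing the lead-in to all ten.** This fails too, because a patient would then need all four indications together. Section 3, Medical Management, joins its grounds for operation with *or*: after aneurysms of at least 5.5 cm it continues "whose symptoms persist, whose aneurysms enlarge and are at least 4.5-cm in diameter, or who develop evidence of bleeding". A split list (one indication plus all other items) fits both that text and the anatomical requirements. That the indications are alternatives remains an inference, since section 3 also names aneurysm diameter as required.

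**What the split then touches.**

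1. *Distal fixation.* Section 5 names an iliac site only; both Intended Use lists allow an iliac or aortic site. Implant Procedures describes an aortic distal seal for types 1 and 5, and Case Planning has the distal aorta measured for that seal. A mandatory iliac-only item would bind those patients as well.
2. *Expanded arm.* Its opening sentence admits subjects who do not satisfy primary-arm inclusion; both entry routes that follow then require that they do. Of the 11 listed reasons, 9 mirror a primary-arm exclusion, so satisfying inclusion while having one of these is coherent. The branch-under-5-mm reason opposes an inclusion item. Once branch diameter is mandatory, no patient could satisfy both.
3. *Bounds.* The Intended Use lists require more than 5.5 cm and growth of more than 0.5 cm in 6 months; section 5 accepts exactly those values. Patient Population has age above 18 and life expectancy of at least one year; section 5 has age 18 or above and more than one year. A branch of exactly 5 mm is in neither the primary-arm item (above 5 mm) nor the expanded-arm item (below 5 mm).

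**The case against.** The strongest reply is that nobody would apply the list literally. Section 4 limits the study to type I, II, III and V thoracoabdominal aneurysms. Screening CT evaluates access vessels and whether vessel diameters suit the device, and the exclusions still apply. Staff may well read sections 3 and 4 together with section 5. This stands as a statement about likely practice: entry on age alone is implausible. It does not repair a lead-in that says the opposite of section 3.

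A reader might infer that nothing keeps small branch vessels out of the primary arm. The documents do not support that: section 3 says vessels under 5 mm are excluded from it, and section 5 lists them among the reasons that exclude a patient from it. A reader might likewise infer that urgent or emergent cases can enter the primary arm because its own list omits them. Section 3 and the Expanded Selection text already state that bar.

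It is also fair to say that the branch-diameter conflict in the expanded arm becomes binding only after the split. That is a reason to settle both together. The expanded arm's opening sentence and its entry routes disagree as they stand.

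**Conclusion.** The contradiction between the section 5 lead-in and section 3 is real and textual, and it should be corrected. It covers access, neck length, branch size and distal fixation size. No exclusion restores neck length, landing-zone diameter, distal fixation, age or life expectancy.

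The effect on patients is unknown and may be zero. A reader might infer that unsuitable patients will be enrolled, or that the 26% expected event rate is compromised because it came from subjects meeting primary-study inclusion. The documents show neither: they do not say how the list was applied to those subjects. The 46 pooled subjects, the 26% rate and the 50% performance goal are unchanged.

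The conclusion assumes that the lead-in governs the whole list, which the unbroken layout supports, and that the indications are meant as alternatives, which the sponsor must confirm.

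**What to change.** In one amendment, split the section 5 list into:

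- (A) at least one of the aneurysm indications; and
- (B) all of access, proximal landing zone, branch diameter, distal fixation, age and life expectancy.

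The sponsor should confirm (A), because section 3 also names aneurysm diameter as required. It should also confirm that the whole landing-zone item is mandatory: sections 3 (Justification) and 4 (Case Planning) require only the length, not the diameter range or celiac distance.

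Reconcile at the same time, with the choice of wording left to the sponsor:

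1. the distal fixation site, between section 5, the two Intended Use lists and the aortic seal described for types 1 and 5;
2. the expanded-arm entry wording, stated once, so that the branch-under-5-mm reason can still admit patients;
3. the bounds for 5.5 cm, 0.5 cm, age, life expectancy and a branch of exactly 5 mm.

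Optional tidying: list urgent or emergent presentation among the primary-arm exclusions, correct the section 6 pointer, and state whether four-vessel patency, which section 3 calls required, is an inclusion item, since section 5 has none.

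The cost is one wording amendment with no change to sample size. It is not purely editorial: part (A), the full landing-zone item, the fixation site and the bounds could change who is eligible, so they need a sponsor decision.
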